23. APPENDIX IV. SAMPLING FOR POTENTIAL BIOMARKER ANALYSIS AND SAMPLE HANDLING GUIDELINES

Please refer to the Laboratory Investigator Manual for all collection and shipping instructions.

BLOOD SAMPLES FOR POTENTIAL BIOMARKER ANALYSES

All collection devices, labels, and requisitions will be provided by the central laboratory.

Plasma Samples

Collect the blood sample in a 4-mL K₂EDTA Vacutainer[®] (or equivalent) tube for the preparation of plasma. The anticoagulant is ethylene diamine tetraacetic acid (EDTA) for plasma samples. Within **5 minutes** of drawing blood, the blood sample will be centrifuged for 15 minutes at ca. 1,000 – 1,200 g to isolate plasma at refrigerated conditions (recommended if available).

If the sample will not be centrifuged promptly, it must be kept on ice until it is centrifuged.

Transfer 2 aliquots of plasma into 2 prelabeled cryovials (PD-Plasma Set 1 and PD-Plasma Set 2) immediately after centrifugation.

Store samples at -70 C prior to shipping to the central laboratory (within 15 min of plasma transfer). If samples cannot be stored at -70°C, refer to the Laboratory Investigator Manual for appropriate storage and shipping instructions.

Serum Samples

Collect blood in a 4-mL serum separator tube and allow clotting for 30 to 60 minutes at room temperature before centrifugation. Within 1 hour of collection, centrifuge for 10 minutes at ca. 2,000 g. Transfer 2 aliquots of serum into 2 prelabeled cryovials (PD-Serum Set 1 and PD-Serum Set 2) immediately after centrifugation.

Store samples at -70°C prior to shipping to the central laboratory (within 15 min of serum transfer). If samples cannot be stored at -70°C, refer to the Laboratory Investigator Manual for appropriate storage and shipping instructions.

Blood (biomarker in plasma and serum) samples will be collected from study subjects at the time points indicated in Table 9.

Table 9: Schedule for Blood (Plasma and Serum) for Biomarker Analysis

| Specimen | Week (Day) |
|------------------------------|---|
| Plasma (Anticoagulant: EDTA) | Baseline visit (Day -1) |
| Serum | Week 12 (Day 84 ±1) or End of Treatment |

Shipping:

Shipment to the appropriate Central Laboratory of PD-Set 1 Plasma and Serum samples will be done separately from shipment of PD-Set 2 Plasma and Serum samples.

Refer to the LABORATORY Investigator Manual for additional collection instructions and detailed procedures.

24. APPENDIX V. PHARMACOGENETIC SAMPLING AND SAMPLE HANDLING GUIDELINES

Please refer to the Laboratory Investigator Manual for all collection and shipping instructions.

BLOOD SAMPLES FOR PHARMACOGENETICS/PHARMACOGENOMICS

- A blood sample (approximately 4 mL) will be collected from each subject using a 4 mL Vacutainer® (or equivalent) collection tube containing EDTA as an anticoagulant.
- The tubes containing the blood sample will be labeled with a unique barcode (if possible), protocol number, subject number, and sample date of collection.
- The blood samples will be kept on wet ice during transfer and labeling.
- All blood samples will be stored in an upright position within 10 minutes of collection in a freezer set to maintain -70°C ($\pm 10^{\circ}\text{C}$) until shipment to the appropriate laboratory. If samples cannot be stored at -70°C , refer to the Laboratory Investigator Manual for appropriate storage and shipping instructions.
- Freeze samples for at least several hours before shipping to the appropriate laboratory.

25. APPENDIX VI. CLINICALLY RELEVANT CYP2B6 SUBSTRATES OR INDUCERS OR INHIBITORS (GENERIC NAMES)

The following drugs are prohibited during this study.

| Substrate | Inhibitor | Inducer |
|------------------|------------------|----------------|
| artemisinin | clopidogrel | artemisinin |
| bupropion | thiotepa | carbamazepine |
| cyclophosphamide | ticlopidine | efavirenz |
| efavirenz | voriconazole | nevirapine |
| ifosfamide | | phenobarbital |
| ketamine | | phenytoin |
| meperidine | | rifampin |
| methadone | | |
| nevirapine | | |
| propafol | | |
| selegiline | | |
| sorafenib | | |

Flockhart DA. Drug Interactions: Cytochrome P450 Drug Interaction Table. Indiana University School of Medicine (2007). <http://medicine.iupui.edu/clinpharm/ddis/table.aspx>. Accessed 4 March 2016.

26. APPENDIX VII. ABUSE POTENTIAL MONITORING PLAN

Overview of Abuse Potential Monitoring Plan

Dasotraline is a new chemical entity being investigated for the treatment of Binge Eating Disorder (BED). Dasotraline is a diastereomer of the major metabolite of sertraline but is not a metabolite of sertraline, nor is it converted to the demethylated metabolite of sertraline in vivo. Dasotraline is a potent inhibitor of the reuptake of serotonin (5-HT), norepinephrine (NE), and dopamine (DA) via the respective transporters SERT, NET, and DAT, with preferential inhibition of the dopamine transporter (DAT) and norepinephrine transporter (NET) relative to the serotonin transporter (SERT) without significant off-target activities. Clinical studies demonstrated central SERT occupancies in healthy subjects well below those attained at DAT, in addition decreases in 3,4-dihydroxyphenylglycol (DHPG) were observed, indicating central NET inhibition. This pharmacological profile warrants the implementation of an Abuse Potential Monitoring Plan, which surpasses the clinical monitoring, and adverse event (AE) reporting historically implemented in development programs for SSRIs.

The Abuse Potential Monitoring Plan (APMP) for dasotraline has been designed to detect potential abuse of the compound and to more closely monitor AEs consistent with the pharmacology. The plan will detect irregularities in the handling of dasotraline in clinical trials and identify the misuse of dasotraline or other psychoactive substances. Moreover, the APMP provides a process by which events subject to additional monitoring are identified, processed, and reviewed. Events subject to additional monitoring were identified based on the pharmacology of dasotraline, as well as adverse event profiles of compounds with similar mechanisms of action.

Procedure for Managing Medication Irregularities

Defining Threshold Criteria

The purpose of this procedure is to capture information about all medication-handling irregularities that meet the predefined threshold criteria. All instances meeting the medication irregularity threshold criteria will require a clinical risk assessment by the Investigator with classification of the nature of the irregularity. The Investigator will be required to complete Attachment A, the Medication Handling Irregularity (MHI) form in these situations.

For clinical trials utilizing dasotraline, we define the threshold criteria for medication irregularities as any one of the following:

- 10% or more of dispensed drug is either used in excess of prescribed dose or is unaccounted for; **and/or**
- Suspected abuse or diversion of dasotraline; **and/or**
- Suspected abuse of any other substance including alcohol, illicit substances, and over-the-counter (OTC) medications or prescription drugs.

Instances of Medication Irregularity

For all instances where the predefined threshold criteria are met covering medication irregularities, the Investigator must complete the Medication Handling Irregularity (MHI) form ([Attachment A](#)) and fax to the contact provided within 3 business days of its occurrence or discovery every time a threshold medication handling irregularity occurs. The contact will fax the completed MHI form to Sunovion within 1 business day of receipt and determine whether further action is warranted (ie, discontinuation of subject due to noncompliance with study protocol, education of the subject, etc.). [Attachment B](#) displays the process flow for handling medication irregularities. Any instance of medication irregularity may further be classified as an event subject to additional monitoring (ESAM).

The management of documented medication handling irregularities will be driven by the particular classification of the irregularity. As shown on Attachment A, items coded #1-3 describe situations of accounting errors and/or noncompliance with study procedures without evidence of study medication misuse or abuse of other substances. In these instances (code #1-3 on the MHI form), the Investigator will complete Attachment A and fax to the contact provided within 3 business days of knowledge of the irregularity.

Suspected or Known Abuse or Diversion of Study Medication

All cases of suspected or known abuse or diversion of study medication should be documented on the MHI form and coded #4. The Investigator will complete Attachment A and fax to the contact provided within 3 business days of knowledge of the irregularity. For all cases of medication irregularities coded as #4, the Investigator will attempt to obtain a urine drug screen from the subject, perform early termination procedures and discontinue the subject from the study.

Suspected or Known Abuse of Alcohol or Other Substances

The abuse of alcohol, illicit substances, OTC medication or prescription drugs while a subject is participating in a dasotraline clinical trial should be documented on the MHI form and coded #5. The Investigator will complete Attachment A and fax to the contact provided within 3 business days of knowledge of the irregularity. For all cases of medication irregularities coded as #5, the Investigator will attempt to obtain a urine drug screen from the subject, perform early termination procedures and discontinue the subject from the study.

Event Subject to Additional Monitoring (ESAM)

A key objective of the Abuse Potential Monitoring Plan is to monitor for instances of abuse or diversion of the study medication and other psychoactive substances. In addition to monitoring for irregularities in medication handling, AEs that may be suggestive of a developing abuse issue, will also receive special attention. The following adverse experiences or related signs and symptoms may be associated with increased risk to subjects and will require additional monitoring. This list is a guide as to the types of events that require additional medical surveillance; it is not comprehensive and other events may be identified that require similar

medical surveillance. Subjects experiencing an event subject to additional monitoring may need to be discontinued from the study.

Table 10: Sample List of Events Subject to Additional Monitoring

| | |
|----------------------------------|---|
| Abuse and Dependence | Perceptual Effects |
| Drug dependence | Abnormal dreams |
| Drug abuse | Disinhibition |
| Dependence | Disorientation |
| Drug diversion | Dissociation |
| Intentional drug misuse | Feeling abnormal |
| Substance abuse | Hallucination (including auditory, olfactory, visual, etc.) |
| Mood Elevation Effects | Hyperaesthesia |
| Euphoric mood | Hypoaesthesia |
| Elevated mood | Illusion |
| Feeling drunk | Inappropriate affect |
| Sedative Effects | Mood altered |
| Apathy | Paraesthesia |
| Asthenia | Paranoia |
| Depressed level of consciousness | Psychotic Disorder |
| Fatigue | Sensory disturbance |
| Feeling of relaxation | Thinking abnormal |
| Hypokinesia | Cognitive/Motor Impairment |
| Indifference | Ataxia |
| Lethargy | Amnesia |
| Sedation | Aphasia |
| Sluggishness | Balance disorder |
| Somnolence | Clumsiness |
| Stimulant Effects | Cognitive disorder |
| Agitation | Confusional state |
| Aggression | Coordination abnormal |
| Anxiety | Disturbance in attention |
| Energy increased | Gait disturbance |
| Feeling jittery | Fine Motor Delay |
| Hypervigilance | Memory impairment |
| Insomnia | Mental impairment |
| Irritability | |
| Nervousness | |
| Psychomotor hyperactivity | |
| Restlessness | |

Preparation of a Narrative for an Event Subject to Additional Monitoring (ESAM)

To ensure clarity and completeness of information, all Events Subject to Additional Monitoring will require the preparation of a narrative by the Investigator. This narrative will be reviewed by the medical monitor/sponsor/Investigator to determine if the subject should be discontinued from the study. A narrative summary template will be provided to the Investigators ([Attachment C](#)).

Handling of the Event Subject to Additional Monitoring (ESAM)

- Investigators will report all Events Subject to Additional Monitoring with narratives to the Medical Monitor within 24 hours ([Attachment C](#))
- The medical monitor will review all ESAM in real time and forward a copy of the report to the sponsors' Medical Director within one business day

Urine Drug Screens

The protocol incorporates exclusion criteria targeting individuals with a history of substance use disorders (eg, alcohol abuse or dependence and illicit drug abuse or dependence). The protocol includes urine drug screens at screening and at various post-randomization visits as well as providing the Investigator with the discretion to obtain random urine drug screens. Investigators will be directed to obtain urine drug screens in instances where there is known or suspected abuse of study medication and/or other substances.

ATTACHMENT A (Part 1 of 2) Medication Handling Irregularity Instructions & Form**INSTRUCTIONS:****Medication Handling Irregularity Involving Subjects in Clinical Trials**

The form is designed to capture information about **threshold** medication handling irregularities to be used in clinical risk assessment. This form must be completed every time a threshold event occurs, within 3 business days of the event and FAXED or EMAILED to the INC medical monitor, [name] at [[name]]([contact]) or [contact].

[contact]

EMAIL: [contact]

Investigator Instructions For Each Event:

- INC's medical monitor must receive a completed Medication Handling Irregularity form by FAX or EMAIL within 3 business days of its occurrence or discovery every time a threshold medication handling irregularity occurs.
- Record any Adverse Event that was associated with, or resulted from, a medication handling irregularity, using the Electronic Case Report Form (Medidata).
- Information on concomitant medications must be recorded on the Concomitant Medication form in the electronic Case Report Form.

ATTACHMENT A (Part 2 OF 2) MEDICATION HANDLING IRREGULARITY FORM

Study No.: SEP360-321 Site No.: _____ Subject No.: _____

Date of Event Discovery: _____

| Date of Event dd-mmm-yyyy | Medication | Threshold | Strength of Medication | Number of Capsules |
|---------------------------|------------|-----------|------------------------|--------------------|
| | | | | |
| | | | | |

Please classify this medication handling irregularity by checking boxes 1 – 5.

1. Drug accounting errors, not involving suspected abuse or diversion by subject.

Describe. (any missing/lost/not returned/unaccounted for blister cards/pills ≥ 10% dispensed)

2. Non-compliance with study procedures, not involving suspected abuse or diversion by subject.

Describe. (subjects who take ≥ 10% more than the prescribed dose, in error)

3. Other cases not involving suspected abuse or diversion of study drug by subject.

Describe. (other qualifying events not categorized by 1 or 2 above)

If only items 2 or 3 are checked, sign and date, and FAX or EMAIL this form to INC Research within 3 business days of its occurrence or discovery. [contact] or EMAIL: [contact]

4. Suspected or known abuse or diversion of any drug. Please describe.

5. Suspected abuse (nonmedical use) of alcohol, illicit substances, OTC or prescription drugs obtained outside study protocol. Please describe.

[figure not shown]
If items 4 or 5 are checked, the investigator will:

- 1) Obtain a Urine Drug Screen from the subject and document the results;
- 2) Complete Early Termination procedures, discontinue the subject from the trial;
- 3) FAX or EMAIL this form to Medical Monitor within 3 business days of its occurrence or discovery. [contact] or EMAIL: [contact]

Investigator Signature _____ Printed Name _____ Date _____

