7.4.8.3.1 Medication Handling Irregularities

Medication handling irregularities will be summarized using the following categories:

- Drug accounting errors, not involving suspected abuse or diversion by subject
- Non-compliance with study procedures, not involving suspected abuse or diversion by subject
- Other cases not involving suspected abuse or diversion by subject
- Suspected or known abuse or diversion of study drug
- Suspected abuse (nonmedical use) of alcohol, illicit substances, OTC drugs or prescription drugs obtained outside the study protocol

Instances that meet the threshold criteria for a medication handling irregularity will be summarized descriptively. Both the number of instances and the number (%) of subjects experiencing medical drug irregularities will be provided for each category and by treatment. Instances of medication handling irregularity will be listed for all randomized subjects.

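### Box 4 of the medication irregularity form covers any drug, while the protocol text and the SAP limit that category to study drug, so misuse of other drugs could be counted as study-drug abuse or diversion

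*Protocol*

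**What the plan says.** Three places define the fourth type of medication irregularity.

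- **Protocol Appendix VII, text.** "All cases of suspected or known abuse or diversion of study medication should be documented on the MHI form and coded #4". For other substances, "The abuse of alcohol, illicit substances, OTC medication or prescription drugs" by a subject taking part "in a dasotraline clinical trial should be documented on the MHI form and coded #5".
- **Protocol Appendix VII, Attachment A, Part 2 (the form sites complete).** Box 4 is "Suspected or known abuse or diversion of any drug". Box 5 is "Suspected abuse (nonmedical use) of alcohol, illicit substances, OTC or prescription drugs obtained outside study protocol". Both ask for a description, and the form has a column naming the medication. A footer tells sites to enter the data in the eCRF.
- **SAP Section 7.4.8.3.1.** The fourth category is "Suspected or known abuse or diversion of study drug" and the fifth is "Suspected abuse (nonmedical use) of alcohol, illicit substances, OTC drugs or prescription drugs obtained outside the study protocol". On reporting: "Both the number of instances and the number (%) of subjects experiencing medical drug irregularities will be provided for each category and by treatment". A listing of instances for all randomized subjects is also planned.

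Assessing abuse potential through the monitoring plan is one of the other secondary objectives (Protocol Section 5.3).

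**The concern.** The form is the data source, and its box 4 is wider than the category it appears to feed. An investigator who learns of cannabis, opioid or stimulant misuse can justify ticking box 4 from the words on the form. If that tick passes unchanged into the SAP's fourth category, the table shows an instance of study-drug abuse or diversion that was nothing of the kind.

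The affected row is a direct summary of observed misuse of study drug, and it serves a stated objective. Protocol Section 4.3 says that no signal of abuse, dependence or withdrawal has been detected in earlier studies, so few true entries are to be expected. In a row with few true entries, a small number of misfiled forms can change how it reads, in either active arm or on placebo.

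**Working it through.** The plan states no figure to reproduce, and the point rests on wording. The check sets the category definitions side by side.

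| Source | Fourth category | Fifth category |
|---|---|---|
| Appendix VII text | suspected or known; abuse or diversion; study medication | heading says suspected or known; abuse; alcohol and other substances |
| Form (Attachment A, Part 2) | suspected or known; abuse or diversion; **any drug** | suspected only; abuse; alcohol and other substances |
| SAP 7.4.8.3.1 | suspected or known; abuse or diversion; study drug | suspected only; abuse; alcohol and other substances |

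**Step 1: scope of box 4.** Of the three sources, only the form does not limit the fourth category to study drug. Two further places in the appendix point the same way as the text. The threshold criteria list dasotraline separately from all other substances, and box 3 of the form itself refers to study drug.

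**Step 2: overlap.** Any drug includes illicit, over-the-counter and prescription drugs. Suspected abuse of one of these fits both box 4 and box 5, and the form gives no rule for choosing between them.

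**Step 3: cases that fit only box 4.** Box 5 speaks of suspected abuse and omits both known abuse and diversion. Read literally, known abuse of a non-study drug, or diversion of one, has only box 4. The appendix heading for code 5 does include known abuse. It does not mention diversion, so the appendix assigns diversion of a non-study drug to neither code.

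**Step 4: how such a case could arise.** Urine drug screens are scheduled at Weeks 6, 12, 13, 14 and 15 (Protocol Table 2). The panel in Appendix II includes cannabinoids, cocaine, opiates and amphetamines. A site that regards a positive screen as known rather than suspected abuse is led by the form's wording to box 4.

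**Step 5: the path to the table.** The SAP cites no box or code numbers. Its five categories do follow the five boxes in order and in nearly the same words, the main change being the drug named in the fourth. The link from box 4 to the fourth category is therefore a reasonable inference, not a stated rule. The SAP contains no mapping rule, no review of box 4 entries and no recoding step. Section 7.4.8.3 says only that sites provide the results before lock and that they are listed.

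**Step 6: size.** The documents give no rate for misfiling. The effect of a single case can be worked out: with 160 subjects planned per arm, one misfiled subject adds one instance and 1/160 = 0.00625, about 0.6 percentage points, to that arm's row.

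**The case against.** The strongest reply is that a site following the protocol codes correctly. Box 5 sits directly below box 4 and names the other substances, and the appendix text assigns them to code 5. Most readers would also treat known abuse as included in suspected abuse. This stands, and it makes miscoding a possibility rather than a prediction. A reader might infer that other drug misuse will be tabulated as dasotraline abuse. The documents do not support that: sites have a route to the right box, the eCRF wording is not available, and the SAP defines its row by content.

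Second, a wrong entry could be seen. The form names the medication and asks for a description, it goes to the medical monitor, and every instance is listed. This also stands, but nothing requires anyone to compare the box with the named drug, and the summary counts would remain as they were.

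Third, a reader might take any placebo count in this row as a false event. Protocol Table 4 defines study drug to include placebo, so abuse or diversion of blinded placebo capsules is a legitimate entry.

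Fourth, a reader might infer that box 1 reports go unsent, because the form's submission line names only boxes 2 and 3. Part 1 of Attachment A requires a form within 3 business days of every threshold event, and the appendix text repeats this for codes 1 to 3. There is no reporting gap.

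Finally, the table is descriptive and not the only output on abuse potential. Events subject to additional monitoring and urine drug screens are reported separately (SAP Sections 7.4.8.3.2 and 7.4.3.1). That limits the consequence but does not remove the conflict.

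**Conclusion.** The inconsistency is real and should be corrected. Box 4 is wider than the category in the protocol text and the SAP, it overlaps box 5, and known abuse or diversion of a non-study drug literally fits box 4 alone. Such cases could be counted by arm as study-drug abuse or diversion, with no written step to catch them.

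The consequence rests on two assumptions: that some sites follow the form's words rather than the appendix text, and that box 4 entries pass unchanged into the SAP's fourth category. Neither can be confirmed or excluded from the documents. The number of cases cannot be derived, and any figure per arm would be a guess. The effect is confined to a descriptive safety table. Efficacy analyses, type I error and sample size are untouched. Subject handling is the same whichever box is ticked, because boxes 4 and 5 share one action list.

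**What to change.** 1. Limit box 4 to study medication, for example by adopting the SAP's own label, "Suspected or known abuse or diversion of study drug".
2. Reword box 5 to cover suspected or known abuse or diversion of all other substances. Including known abuse follows the appendix heading. Including diversion closes the case that the appendix leaves without a code.
3. State in SAP Section 7.4.8.3.1 which form box feeds each category, and that the fifth category takes the same scope as the revised box 5.
4. Before database lock, compare every box 4 entry, blind to arm, with the medication column and the description. Move any entry about a non-study drug to the fifth category and record the change.

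The SAP already reports enrolment as complete (Section 6.1.7), so rewording may come too late for many forms. Step 4 is the part that protects the table. The cost is one form edit, a short site memo, a sentence or two in the SAP and a brief blinded review.
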